7.2 SECONDARY OUTCOMES

The following will be assessed as secondary outcomes

- Brain behavior correlation to account for inter-participant variance. For the significant behavioral findings, we will correlate the strength of phase amplitude coupling during the post-stimulation rest period with the impact on behavior.
- For the significant behavioral findings, brain behavior correlation between the strength of phase amplitude coupling in the baseline session to the behavioral effect of CF-tACS on task performance.

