2.4 STUDY AIMS/HYPOTHESES

The purpose of this pilot study is to evaluate the potential efficacy of using CF-tACS to modulate cortical oscillations observed during cognitive tasks, to generate hypotheses, and to obtain statistical estimates and other information needed for planning a subsequent larger-scale study.

Aim 1. Characterize CF-tACS effects in terms of the outcome measures of interest.

Aim 2. Perform exploratory analyses to generate new hypotheses.

Aim 3. Obtain preliminary data and population parameter estimates needed to plan a future study.

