3 SUBJECT SELECTION AND WITHDRAWAL

A total of 24 participants will be recruited for this study and all data will be collected at UNC-CH. No specific plans have been made to enroll participants from vulnerable populations.

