12.2 STATISTICAL ANALYSIS PLANS

Statistical analyses will be performed to test the null hypothesis indicated in section 2.4 *Study Aims/Hypothesis*.

The cognitive task will consist of 400 trials. The EEG recorded simultaneously with the task will be analyzed following an established preprocessing pipeline to remove artifacts related to eye movements, eye blinks, heart beats and muscle activity. The oscillation power and phase will be estimated using Morlet wavelet convolution. The primary outcome is phase-amplitude coupling between the stimulated frequencies (measured from EEG), reaction time, and accuracy. Phase amplitude coupling will be calculated as the phase locking value corrected for spurious noise using a boot-strapped null distribution (see Cohen Analyzing Neural Time Series Data 2014 for method).

Our primary outcomes and their test are described below:

- Theta-gamma tACS will increase theta-gamma phase amplitude coupling (one-tailed, Student's t-test)
- Delta-beta tACS will increase delta-beta phase amplitude coupling (one-tailed, Student's t-test).
- Theta-gamma tACS will alter behavior (reaction time or accuracy) as a function of set-size relative to sham-tACS (Student's t-test).
- Delta-beta tACS will alter behavior (reaction time or accuracy) as a function of abstraction relative to sham-tACS (Student's t-test).

As exploratory analysis, linear mixed-effects models with BDNF genotype, sex hormone levels, as factors in addition to the variables condition and period will be fit with the rest of the analysis following what is described for primary analysis.

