12.3 SAMPLE SIZE DETERMINATION

Based on the study by Alekseichuk et al 2017 which investigated the effect of CF-tACS on task accuracy and resting state EEG connectivity in 20 healthy participants per crossover arm, we conjecture that our effect size is at least 0.48. With this effect size, our sample size of 24 has power greater than 60% with alpha 0.05. We have improved upon the experimental design in Alekseichuk et al 2017 by personalizing our stimulation frequencies to target the frequencies of peak phase-amplitude coupling during the task. With this methodological improvement, we expect our effect size to increase to 0.6 (see Romei et al. 2016). With this effect size, our sample size has power greater than 85%.

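### Both secondary brain-behaviour correlations are run only after a significant group behavioural effect, a condition their purpose does not need and which can withhold estimates the pilot is meant to supply

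*Combined protocol and SAP*

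**What the plan says.** Section 7.2 lists two secondary outcomes. The first is introduced as "Brain behavior correlation to account for inter-participant variance" and continues: "For the significant behavioral findings, we will correlate the strength of phase amplitude coupling during the post-stimulation rest period with the impact on behavior". The second carries the same condition: "For the significant behavioral findings, brain behavior correlation between the strength of phase amplitude coupling in the baseline session" is to be related to the behavioural effect of stimulation.

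The findings that must be significant are the group behavioural tests in Sections 7.1 and 12.2. For theta-gamma stimulation, Section 12.2 reads: "Theta-gamma tACS will alter behavior (reaction time or accuracy) as a function of set-size relative to sham-tACS (Student's t-test". Delta-beta has the matching test on abstraction. Neither section gives the sidedness of these behavioural tests or a multiplicity rule.

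Section 12.2 does not mention the correlations, so it neither lifts the condition nor gives a fallback. The other planned analyses of individual differences (Sections 7.3 and 12.2) use genotype, hormone levels and self-report measures. None relates coupling to the behavioural effect.

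Section 2.4 describes a pilot. It includes "Aim 2. Perform exploratory analyses to generate new hypotheses", and Aim 3 is to obtain preliminary data and parameter estimates for a later study. Section 12.3 states, for an effect size of 0.48: "With this effect size, our sample size of 24 has power greater than 60% with alpha 0.05".

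**The concern.** A correlation between coupling and behavioural change describes how people differ around the group mean. It can be strong when the mean is zero and absent when the mean is large. A t-test on the mean is therefore a poor screen for whether the correlation is worth estimating.

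The screen also works against the stated reason for the first correlation. Larger differences in response between people widen the standard deviation of the within-person contrast. For a given raw mean, that lowers the t statistic and makes a significant result less likely. The protocol expects such differences: Section 2.1 gives the possible genetic dependence of response as the reason for genotyping.

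At stake are the only planned estimates linking coupling to behaviour. If the plan is followed as written, the later study may be designed without them, or with those for some contrasts only, chosen by p-value.

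**Working it through.** **Inputs from the plan.** There are 24 participants in a crossover (Sections 3 and 4), hence 24 within-person differences per contrast. Alpha is 0.05, and the effect sizes are 0.48 and 0.6 (Section 12.3). Section 4.1.2 excludes dropouts and reuses their codes, so 24 is kept as the analysed number.

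**Assumptions.** The behavioural tests are taken as two-sided. The true correlation is set at 0.4, because the documents give none. Smaller mean effects of 0.3 and 0 are added to show the range.

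**Step 1: the plan's own figure.** The power of a paired t-test comes from the noncentral t distribution with 23 degrees of freedom and noncentrality d × √24. At d = 0.48 the noncentrality is 0.48 × 4.899 = 2.35, and two-sided power is 61.5%. This agrees with the stated figure of more than 60%. At d = 0.6 two-sided power is 80.4%, below the stated 85%; one-sided power is 88.6%. The sidedness behind Section 12.3 is thus unclear, and Step 2 gives both.

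**Step 2: how often the correlation is run for one contrast.** This equals the power of the behavioural test.

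| Mean effect d | Run, two-sided | Skipped, two-sided | Run, one-sided |
|---|---|---|---|
| 0 | 5% | 95% | 5% |
| 0.3 | 29% | 71% | 41% |
| 0.48 | 62% | 38% | 74% |
| 0.6 | 80% | 20% | 89% |

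**Step 3: several contrasts.** Two regimens with two measures each (reaction time and accuracy) give four contrasts, each with its own condition. If the four tests are independent, the chance that at least one is significant is 1 − (1 − p)^4:
- d = 0.48: 1 − 0.385^4 = 98%
- d = 0.3: 1 − 0.709^4 = 75%
- d = 0: 1 − 0.95^4 = 18.5%

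With an assumed correlation of 0.8 among the contrasts, the first two figures become 79% and 47%.

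**Step 4: detecting a true correlation of 0.4.** These figures come from simulation (200,000 trials per scenario, bivariate normal data, both tests two-sided at 0.05). Without the condition, detection is 51% whatever the mean effect.

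| Mean effect d | Run and significant | Significant, given that it is run |
|---|---|---|
| 0 | 2% | 44% |
| 0.3 | 14% | 47% |
| 0.48 | 30% | 49% |
| 0.6 | 40% | 49% |

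Almost all the loss comes from the correlation not being run.

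**Step 5: false positives when the true correlation is zero.** A correlation that is run keeps a level near 5%. Counted over all trials, the rate is 0.05 × P(run): 0.05 × 0.615 = 3.1% at d = 0.48, 0.05 × 0.291 = 1.5% at 0.3, and 0.05 × 0.05 = 0.25% at 0.

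**Step 6: heterogeneity.** Hold the raw mean at 0.48 with residual standard deviation 1, and let the true response vary between people with standard deviation τ (assumed). The standardised effect is 0.48/√(1 + τ²).
- τ = 0: 0.48, run 62% of the time
- τ = 1: 0.34, run 36%
- τ = 2: 0.21, run 17%

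**The case against.** The strongest defence is that the condition is stated in advance and limits the number of correlations tested in a small study. That stands in part. A reader might infer that the condition does nothing for error control because each correlation that is run keeps its 5% level. Step 5 shows otherwise: over all trials it produces fewer spurious correlations.

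A reader might also take 61.5% as the chance that any correlation is run. The documents do not support that, because the condition applies to each finding separately and there are several findings. Step 3 gives 79% to 98% for at least one at an effect of 0.48.

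Nor does the condition inflate the behavioural effects. Those contrasts are primary outcomes, tested and reported whatever happens to the correlations. Among significant results at a true effect of 0.48 the observed effect averages about 0.63, but that is ordinary selection on significance, and removing the condition would change no behavioural estimate.

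Finally, the stated purpose appears only in the first bullet and could mean explaining variance around an effect already shown. Aim 2 leaves room for an unplanned exploratory correlation, so the analysis is not forbidden after a null result. It is only not planned. These points limit the size of the concern but do not show why an estimation pilot needs the condition.

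**Conclusion.** The concern holds as a modest one about a secondary analysis. Section 7.2 ties both planned coupling-behaviour estimates to a group p-value that is not relevant to them, and nothing elsewhere in the document provides a substitute. Per contrast, the estimate is lost about 38% of the time at the protocol's base effect and 20% at its optimistic one. For an assumed correlation of 0.4, the chance of running and detecting it falls from 51% to 30% and 40% respectively.

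These figures rest on a two-sided test, 24 complete participants and normal data. Under one-sided behavioural tests the losses are smaller (about 26% and 11% skipped). The correlation of 0.4 and the heterogeneity values are illustrations. The reasoning against the condition does not depend on them.

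**What to change.** In Section 7.2, delete the opening restriction to significant findings from both bullets. Name the behavioural contrasts in advance. Compute both correlations for each regimen and each primary behavioural contrast whatever the group p-value, and report each r with a 95% confidence interval as a secondary estimate, without a significance claim. Repeat this in Section 12.2.

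No new participants, visits or measurements are needed: Sections 5.2 and 5.4.1 and Appendix A already provide for the baseline session, the rest EEG and the task data.

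The cost is up to 2 regimens × 2 measures × 2 coupling predictors = 8 estimates. Read as tests at 0.05, and if independent, they would give at least one false positive with probability 1 − 0.95^8 = 34%. Interval reporting deals with this and shows how little 24 people can say. By the Fisher transformation, atanh(0.4) ± 1.96/√21 gives an interval of about 0.00 to 0.69 for an observed r of 0.4. A Holm step is possible, but at its first threshold (0.05/8) power for a true correlation of 0.4 drops to about 21%, so it suits this pilot less well.

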7.3 EXPLORATORY OUTCOMES

Additionally, the following exploratory measures will be assessed

- Modulation in spectral power in other frequency bands (1 – 4 Hz; 8 – 12 Hz; 12 – 30 Hz; 30 – 50 Hz) of CF-tACS
- Coherence between distant regions of the brain in the slower frequency of the CF-tACS coupled pair (delta and theta)
- Hormone level and BDNF as covariates in analysis of differences in spectral power
- Self-reported anxiety, affect and sleep quality as covariates in the analysis of differences in spectral power

8 STUDY INVESTIGATIONAL PRODUCT

8.1 DEVICE DESCRIPTION

Participants will be stimulated with the commercial, CE-certified NeuroConn Plus stimulator. The use of this device in this study has previously received a NSR designation on initial review by the full UNC IRB. The NeuroConn device description is as follows:

The DC-STIMULATOR is a CE-certified medical device for conducting non-invasive transcranial direct-current stimulation (tDCS) in humans. DC stimulation is used in clinical practice and in the research of stroke, epilepsy, migraine, tinnitus, depression, multiple sclerosis, dementia and chronic headache. The DC-STIMULATOR is a micro-processor-controlled constant current source. It meets the highest safety standards thanks to (hardware- and software-based) multistage monitoring of the current path. By continuously monitoring electrode impedance it can detect insufficient contact with the skin and automatically terminate stimulation, maximizing patient safety.

The device's alphanumeric display and the 4 touch keys allow various stimulation modes to be selected and stimulation parameters such as current strength, duration, fade-in and fade-out to be set.

DC-STIMULATOR features:

- 1 channel (anodal and cathodal stimulation possible)
- Adjustable current up to 5,000 μA *
- Adjustable application time up to 30 minutes *
- 2 standard modes - single (continuous stimulation) and - pulse (cyclical stimulation activation/deactivation) with fade in and fade out
- Customer-specific programs possible (optional)
- "Study mode" for blind processing of genuine and 'pseudo' stimulation (optional)
- External trigger input (optional)

8.2 SAFETY FEATURES

The NeuroConn DC Plus stimulator has been cleared for investigational use by the FDA and is CE-Certified. More information can be found in the manual for the stimulator.

8.3 PREPARATION AND ADMINISTRATION OF STUDY INVESTIGATIONAL PRODUCT

After participants have completed the questionnaires, they will be comfortably seated. The research team will first measure their heads electrode placement using the 10-20 system. Participants will then be fitted with the 3 electrodes for stimulation. The participant will be in the relaxed yet, experimentally controlled state with their chin on a chin rest in front of a monitor. Participants will wear earplugs throughout the session to reduce distraction. One session of stimulation will be performed per visit for 40 minutes, in 8 blocks of 5 minutes each. During the verum CF-tACS conditions, participants will have a 10 second ramp in and ramp out with 5 minutes of stimulation for 8 blocks for a total of 2560 seconds. Stimulation waveforms are cross frequency waveforms with a burst of either beta (18-35 Hz) or gamma (30-60Hz) frequency at the peak of a slower oscillations in delta (2-5 Hz) or theta (4-8Hz). The maximum amplitude of stimulation is 2 mA. The sham CF-tACS stimulation will include 10 seconds of ramp in to 20 seconds of CF-tACS with a ramp out of 10 seconds for a total of 40 seconds of stimulation. Electrodes

(3.0 cm x 3.0 cm) will be affixed using electrically conductive ten20 paste and placed over F4 and C4. A single return electrode (5.0 cm x 7.0 cm) will be affixed in the same manner between Cz and Fz.

Our stimulation setup consists of the stimulator controlled by a desktop through a USB DAQ (National Instruments). Stimulation parameters (waveform, duration, amplitude) is set by custom written software application that is preprogrammed for each study. The software receives stimulation codes and generates the stimulation waveform and sends it to the stimulator where the waveform is converted to stimulation current. The mapping between stimulation code and stimulation waveform is hidden from the experimenter and only the study member ([name]) will be able to access this.

The study coordinator and/or the research assistant will be thoroughly trained and have trainings documented on the transcranial stimulation device and will be present during all stimulation sessions. *Please see Appendix F for an example of the training documentation log.* To monitor side effects of stimulation a questionnaire will be administered after each stimulation session. *Please see Attachment 1 for an example of the stimulation questionnaire.*

8.4 ASSESSMENT OF PARTICIPANT COMPLIANCE WITH STUDY INVESTIGATIONAL PRODUCT

Compliance for this study includes attending all four sessions. Individuals who miss the first session (and are unable to reschedule) and/or individuals who miss the second, third or fourth session (and are unable to complete the remaining sessions) will be dropped from the study.

9 POTENTIAL RISKS AND BENEFITS

9.1 BENEFITS TO SUBJECTS AND SOCIETY

The results of this study have implications for the use of CF-tACS as a treatment method for cognitive deficits and other neurological and psychiatric disorders. The results of this study may also prompt further investigation into the relationship between cortical oscillations and brain stimulation waveforms.

This study is not designed to benefit the individual participants.

9.2 POTENTIAL RISKS

8.2.1 PHYSICAL

Risk of Injury and Discomfort: Transcranial current stimulation has been used without any reports of serious side-effects for more than a decade. This stimulation made has NOTHING to do with electroconvulsive therapy that applies many orders of magnitude higher stimulation current. Rather, transcranial current stimulation is so weak that it does not cause super-threshold activation of neurons ([name] and McCormick, 2010). In particular, tACS has been used without reports of any serious side-effects. Some participants report a transient mild tingling, burning, or itching underneath the electrodes and headache, but no other side effects have been noted. Importantly, it remains unclear if these mild side-effects were caused by the transcranial brain stimulation. In order to monitor these side-effects, we will be administering an adverse effects stimulation questionnaire after each stimulation session to determine whether these effects were experienced. Research personnel present during these sessions will also check in with the participant periodically during the stimulation to see whether they are comfortable. If the participant experiences severe discomfort, the stimulation will be immediately stopped and the participant will withdraw from the study.

9.3 REFERRALS FOR MEDICAL FOLLOW-UP OR PSYCHOLOGICAL COUNSELING

There is a purely theoretical likelihood that stimulation of neuronal circuits can lead to epileptic discharge. To minimize this occurrence, we screen and exclude patients with personal and family history of neurological conditions from the study. If abnormalities or a seizure is witnessed during the course of the study, a referral will be made to the UNC Department of Neurology for follow-up. In the theoretical event that a seizure is witnessed that involves the loss of consciousness, the patient will be told not to operate a motor vehicle until cleared by the DMV.

To ensure participant comfort, a study coordinator or research assistant will periodically check in with the participant about any side-effects he/she may be experiencing during each stimulation session. Following the conclusion of the stimulation session, the participant will receive an Adverse Effects Questionnaire to report on any of the side-effects he/she may have experienced. This questionnaire reports side-effects on a likert scale (1=Absent, 2=Mild, 3=Moderate, 4=Severe). If the participant reports side-effects of Moderate to Severe intensity, a study coordinator or research assistant will discuss the side-effects experienced and note this response. If the participant has rated Severe discomfort, the participant will be withdrawn. The PI will be contacted based on the reported intensity on the Adverse Events Questionnaire and the participant's verbal confirmation of intensity.

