4.1.2 DROPOUTS

In case of dropouts, defined as not completing the stimulation part of either visits, data will not be included in the final analysis and the stimulation codes will be reused for the next participants.

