6.3 SAFETY MEASURES

We will be monitoring the safety of our participants throughout the study with the following measures. These measures are listed below and can be found in the attached documents.

- A. A stimulation adverse effects questionnaire used in previous studies (IRB #14-1622, #14-3285, and #14-0600) will be administered at the end of each stimulation session. This questionnaire will be used as a safety measure and to collect data on participant experience. Please see 10.1 *Safety Parameters* for more information.

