10.3 EARLY WITHDRAWAL OF PARTICIPANTS

10.3.1 REASONS FOR WITHDRAWAL

A study participant will be discontinued from further participation if:

- The participant fails to adhere to rules, including stress, exercise, and sleep restrictions

- The participant meets any exclusion criteria (either newly developed or not previously recognized).
- Anything that, in the opinion of the investigator, would place the participant at increased risk or preclude the participant's full compliance with or completion of the study.
- Participants experience severe discomfort during stimulation

Participants are free to withdraw from participation in the study at any time upon request.

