10.3.2 DATA COLLECTION AND FOLLOW-UP FOR WITHDRAWN PARTICIPANTS

We will collect safety data on any participant discontinued because of an AE or SAE. In any case, every effort will be made to undertake protocol-specific follow-up procedures. If an AE has been reported, researchers will help the participant seek the medical care they need and a follow-up will be performed by the PI. In the case of an early withdrawal, the researcher will make a note to file indicating this.

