11.2 METHODS AND TIMING FOR ASSESSING, RECORDING, AND ANALYZING SAFETY PARAMETERS

11.2.1 ADVERSE EVENTS

All AEs, including local and systemic reactions not meeting the criteria for “serious adverse events”, will be captured on the appropriate CRF. In addition, the AE Report Form will be completed by the study coordinator (Appendix B). The AE Report Form includes the following:

- What is known about the therapy
- What is known about previous reported side effects
- If the AE occurred in temporal relation to the therapy
- Whether or not the AE improves or disappears when treatment is stopped
- Whether the AE is worsening of baseline symptoms
- Whether the AE is related to concurrent medical condition or medication use

Once complete, this form will be given to the PI and Co-I, who will review, comment, and sign this form. Completed forms will be placed in the participant’s folder.

In addition, the study coordinator will document any AE occurrence on the AE log (*Appendix D*), which includes information such as the date of the AE, severity, relationship to the treatment (assessed by the PI and Co-I*), actions taken, and outcome(s). The log will be reviewed and initialed by the PI 72 hours after being completed. All AEs occurring during the clinical trial will be documented appropriately regardless of relationship to CF-tACS. All AEs will be followed to adequate resolution and will be graded for severity and relationship to study treatment. Any medical condition noted at the initial session will be considered at baseline and not reported as an AE.

All AEs will be graded for severity using the following guidelines:

CONFIDENTIAL

- **ASYMPTOMATIC.** The participant is exhibiting no symptoms due to this event; no treatment needed.
- **MILD.** Event results in mild or transient discomfort, not requiring intervention or treatment; does not limit or interfere with daily activities (e.g., insomnia, mild headache)
- **MODERATE.** Event is sufficiently discomforting so as to limit or interfere with daily activities; may require interventional treatment (e.g., fever requiring antipyretic medication). In the case of a moderate AE, the medical advisor may recommend an over the counter medication.
- **SEVERE AND UNDESIRABLE.** Event results in significant symptoms that prevent normal daily activities; may require hospitalization or invasive intervention (e.g., anemia resulting in blood transfusion).

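### The dropout rule in section 4.1.2 makes no exception for safety data, so a side-effect summary that follows it would omit participants withdrawn early for severe discomfort

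*Combined protocol and SAP*

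**What the plan says.** **Withdrawal.** Three places withdraw a participant for severe discomfort. Section 9.2 (subsection headed 8.2.1 Physical) covers events during stimulation: "If the participant experiences severe discomfort, the stimulation will be immediately stopped and the participant will withdraw from the study". Section 9.3 covers the questionnaire after the session: "If the participant has rated Severe discomfort, the participant will be withdrawn". Section 10.3.1 lists among its reasons for discontinuation: "Participants experience severe discomfort during stimulation".

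**Exclusion and replacement.** Section 4.1.2 describes dropouts as "defined as not completing the stimulation part of either visits" and says of them that "data will not be included in the final analysis and the stimulation codes will be reused for the next participants". The word used is data, without restriction to EEG or task data.

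**Safety records.** Section 6.3 says of the side-effect questionnaire: "This questionnaire will be used as a safety measure and to collect data on participant experience". Section 10.3.2 says: "We will collect safety data on any participant discontinued because of an AE or SAE". Section 11.2.1 adds: "All AEs occurring during the clinical trial will be documented appropriately regardless of relationship to CF-tACS", with a report form, a log, severity grading and follow-up.

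**Analysis.** Sections 7 and 12.2 define outcomes and tests for coupling, reaction time and accuracy, plus secondary and exploratory EEG and behavioural measures. Neither names a side-effect outcome, table or analysis set. The heading of section 11.2 announces methods for analysing safety parameters, but the text beneath it covers recording, grading and reporting only.

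**The concern.** Read together, the rules make severe discomfort a reason to leave the study, and leaving the study a reason for a participant's data to be left out and the place refilled. Section 4.1.2 is the only rule in the plan on whose data enter an analysis. An analyst who builds a side-effect table by condition and applies that rule would be summarising people selected for not having had the event of most interest. Because the stimulation codes are reused, the reported sample can return to 24 with no visible gap.

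The pilot is meant to feed a larger multi-site study (section 4). Section 2.3 also supports the present stimulation duration partly by pointing to the absence of significant side effects in the group's earlier experiments. A side-effect summary from this trial is therefore likely to be used in the same way.

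**Working it through.** **Figure to reproduce.** The documents give no rate of Severe ratings, withdrawal or dropout, so there is no stated figure to check. The power figures in section 12.3 do not bear on this point.

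**Step 1: which cases fall under 4.1.2.** Stimulation is given at Sessions 2, 3 and 4 (section 5.2 and Appendix A).

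- *Stimulation stopped part-way, at any of these sessions:* the stimulation part is incomplete, so the participant is a dropout.
- *Severe discomfort rated after Session 2 or 3:* the participant is withdrawn and cannot complete the remaining stimulation. Section 8.4 likewise drops those who cannot complete later sessions.
- *Severe discomfort rated after a completed Session 4:* all stimulation is done, so the participant is not a dropout and the data stay in.

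The definition refers to either of two visits, which does not fit three stimulation sessions. The second case therefore rests on the natural reading that all three must be completed.

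**Step 2: how many verum sessions are exposed.** Section 4 lists six sequences, and I assume 24/6 = 4 participants in each. Every participant has two verum sessions, giving 24 × 2 = 48. The last period is active in four sequences (S-At-Ad, S-Ad-At, At-S-Ad, Ad-S-At), so 4 × 4 = 16 verum sessions fall at Session 4. The other 48 − 16 = 32 (67%) fall at Sessions 2 and 3.

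**Step 3: expected cases, for illustration.** Assume a probability *p* of a Severe discomfort rating per verum session, zero under sham, independent between sessions, and every rating made after a completed session. Consider the first 24 participants.

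- Any Severe rating: 24 × [1 − (1 − p)²].
- Withdrawn before completing stimulation: four sequences have one verum session in the first two stimulation periods and two sequences have two, so 24 × {4p + 2[1 − (1 − p)²]}/6.
- Severe only at Session 4: the difference.

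| Assumed p | Any Severe | Dropouts, left out | Session 4 only, kept |
|---|---|---|---|
| 1% | 0.48 | 0.32 | 0.16 |
| 2% | 0.95 | 0.64 | 0.31 |
| 5% | 2.34 | 1.58 | 0.76 |
| 10% | 4.56 | 3.12 | 1.44 |

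About two thirds of the cases would be left out and one third kept.

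**Step 4: effect on a reported proportion.** Suppose two participants are withdrawn for severe discomfort and replaced, and none of the 24 completers rates Severe.

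- Everyone stimulated: 2/(24 + 2) = 2/26 = 7.7%, exact 95% interval 0.9% to 25.1%.
- Completers only: 0/24, two-sided 95% upper limit 1 − 0.025^(1/24) = 14.2%.

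The limits overlap widely, as they must at this size. What changes is that the table shows no case where there were two.

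**The case against.** The strongest reply is that no planned result is affected. Sections 7 and 12 contain no tolerability outcome, and 4.1.2 sits under treatment assignment beside the reuse of codes. Its final analysis is most naturally the analysis in 12.2. This stands: a reader might infer that the trial's tolerability result removes severe cases, but the documents define no such result.

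A reader might also infer that the cases are lost. They are not. Sections 10.3.2 and 11.2.1 keep them in the safety records and AE log, and 9.3 has Moderate to Severe responses discussed and noted. What those sections do not do is say that these participants are counted in a summary by condition.

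A third tempting reading is that every Severe rating removes a participant. A rating after a completed Session 4 does not. Moreover, the trigger in 9.3 is severe discomfort, whereas the questionnaire in 11.1 also covers items such as sleepiness and improved mood. A Severe score on any one item is not clearly a withdrawal trigger.

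Finally, the rates in the working have no support in the text. Section 9.2 reports only transient mild effects, and at 1% fewer than one participant (0.32) would be affected. A bound for 0 of 48 verum sessions, 1 − 0.05^(1/48) = 6.1% one-sided, might be offered as the false reassurance at stake. It treats each participant's two sessions as independent, so I do not rely on it.

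**Conclusion.** The point holds as a conditional one. Section 4.1.2 excludes and replaces dropouts with no exception for safety data, and severe discomfort leads to withdrawal. Any side-effect summary that follows 4.1.2 would therefore omit those withdrawn before completing all three stimulation sessions and would understate severe effects. This rests on the text alone.

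The size cannot be taken from the documents. The 2/26 against 0/24 comparison and the expected counts are illustrations under assumed rates. The 32 of 48 verum sessions assumes equal allocation to the six sequences.

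No planned test, estimate or power figure changes, and the individual cases remain on record. I rate this minor to moderate. It is still worth changing, because it concerns a stated exclusion rule and not merely missing detail.

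**What to change.** 1. In 4.1.2, limit the exclusion of dropouts to the EEG and behavioural analyses.
2. In the same section, reword the dropout definition so that it fits the three stimulation sessions.
3. Add to 12.2: *Side-effect ratings, early stops and withdrawals will be tabulated by the condition received, for every participant who received any stimulation, including those withdrawn or replaced.*

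The passages on withdrawal (9.2, 9.3, 10.3.1), dropouts (4.1.2) and safety records (10.3.2, 11.2.1) should then be read together for consistency. The withdrawal rule itself is left as it is.

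The cost is a few sentences and one table from data already collected. Because codes are reused, the link between each replaced participant and the code used must be kept so that the condition received can be recovered after unblinding. The downside is that the safety table will have a different denominator from the efficacy analysis, which a footnote can explain.
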